3.2.1 Pharmacokinetics: With single doses, absorption

of PF-04457845 is rapid, and concentrations peak (C_{max}) within an average of 2 hours post dose. Elimination of PF-04457845 is multi-phasic, with a half-life (t1/2) ranging from 12-23 hours. With multiple dosing, steady-state plasma concentrations were attained by Day 7. An approximate 2-3 fold accumulation in exposure was observed between days 1 and 14. PK at steady-state appeared dose-proportional. There are no major food effects on PF-04457845. Urine excretion of PF-04457845 as intact parent was negligible. PK is commensurate with QD dosing.

3.2.2 Pharmacodynamics: Peripheral FAAH activity was measured ex vivo in blood leukocytes. Plasma concentrations of anandamide, PEA, OEA and *N*-linoleoylethanolamide (LEA) were measured as pharmacodynamic biomarkers. PEA, OEA, and LEA may have anti-inflammatory, sleep inducing, and appetite inducing effects. Inhibition of FAAH activity and elevation of a number of fatty acids has been demonstrated with single and multiple doses. Pharmacological washout takes 10 days after multiple dosing with 4 mg due to a combination of the time it takes for the drug to clear and the time that it takes for FAAH activity to recover. This slow pharmacological washout may offer the advantage of being less likely to result in withdrawal symptoms.

The effects of 5 doses of PF-04457845 (0, 0.5, 1, 4 and 8 mg) on cognitive function were tested in a randomized, double-blind, placebo-controlled, parallel group study of healthy volunteers (Pfizer; on file). Participants were repeatedly assessed several times a day and several days over 2 weeks using the CogState battery, a battery that assesses psychomotor function, visual attention, learning, executive function, and delayed recall, as well as a global measure of cognition across domains (202). While PF-04457845 was not associated with

changes in cognitive function in healthy adults when given over 14 days, it is not clear what effects it might have on cognitive function in cannabis dependent individuals who are known to have cognitive deficits. Of note, oral THC attenuated some of the cognitive deficits associated with CWS (101).

3.3 Human Phase 2 Osteoarthritis Study: The effects

of 2 weeks of daily oral administration of PF-04457845 on pain relief in patients with osteoarthritis of the knee were

[figure not shown]

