9.9 *Early Termination Study Visit:* If a participant decides to withdraw from the study after randomization or is terminated by the site principal investigator for any reason after randomization, an early termination study visit will be conducted to close out the participant from the study. At this visit the participant will be instructed to return all unused study medication. The Week 9 procedures will be attempted at an early termination visit, which will be conducted per Section 9.7.1, both in person and remotely.

10.0 ASSESSMENTS:

Every effort should be made to ensure that protocol-required tests and procedures are completed as described. When a protocol-required test cannot be performed, study staff will be instructed to document the reason for the missed test and any corrective and preventative actions which s/he has taken to ensure that required processes are adhered to as soon as possible. Any protocol deviations should be documented in the study log.

10.1 Blood: Total blood sampling volume for the individual participants is approximately 420 mL over approximately 14 weeks of the study. The actual times of blood sampling may change. Additional blood samples may be taken for safety assessments at times specified by the Coordinating Center, provided the total volume taken during the study does not exceed 450 mL (safety, PF-04457845 levels, endocannabinoid levels).

10.2 Safety:

10.2.1 Laboratory Tests: The following safety laboratory tests will be performed at the following study visits: Screening, Week 1, Week, 5, Week 7, Week 9, and End of Study Visit (end of Week 12). They are conducted periodically throughout the duration of the study to monitor electrolyte and liver/kidney function. Additional laboratory results may be generated on the samples (without additional blood volume drawn) as a result of the method of analysis, the type of analyzers used, or as derived or calculated values; if such results are available, they may also be reported. Unscheduled clinical labs may be obtained at any time during the study to assess any perceived safety concerns.

Hematology: Hemoglobin, Hematocrit, RBC Count, MCV, MCHC, RDW, MCH, MPV, Platelet Count, WBC Count, Total Neutrophils (Abs), Eosinophils (Abs), Monocytes (Abs), Basophils (Abs), Lymphocytes (Abs); Collected using one 10cc Lavender-top Tube (tube contains EDTA as an anticoagulant).

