Pharmacokinetics: With single doses, absorption of PF-04457845 is rapid, and concentrations peak (Cmax) within an average of 2 hours post dose. Elimination of PF-04457845 is multiphasic, with a half-life (t1/2) ranging from 12-23 hours. With multiple dosing steady-state plasma concentrations were attained by Day 7. An approximate 2-3 fold accumulation in exposure was observed between days 1 and 14. PK at steady-state appeared dose-proportional. There are no major food effects on PF-04457845. Urine excretion of PF-04457845 as intact parent was negligible. PK is commensurate with QD dosing. Phase 1 safety: Several phase 1 studies have been conducted. Safety assessments including adverse events monitoring, physical examinations, 12-lead ECGs, vital signs (blood pressure, pulse rate and body temperature) and laboratory safety tests were conducted at intervals throughout all studies. Continuous cardiac monitoring, via telemetry was conducted up to 8 hours post-dose in the SRD study and up to 4 hours post-dose on Day 1, 7 and 14 of the MRD study. All observed or reported AEs were recorded for all participants and AEs were classified as mild, moderate or severe and their relationship to study drug was assessed by the investigator. As illustrated (Figure 19) the drug and its effects persist for up to 2 weeks after last dose; this is the reason for the 4-week safety follow-up.

Pharmacodynamics: Peripheral FAAH activity was measured ex vivo in blood leukocytes. Plasma concentrations of anandamide, PEA, OEA and *N*-linoleoylethanolamide (LEA) were measured as pharmacodynamic biomarkers. PEA, OEA and LEA have anti-inflammatory, sleep inducing and appetite inducing effects. Inhibition of FAAH activity and elevation of a number of fatty acids has been demonstrated with single and multiple doses. Pharmacological washout takes 10 days after multiple dosing with 4mg due to a combination of the time it takes for the drug to clear and the time that it takes for FAAH activity to recover. This slow pharmacological washout may offer the advantage of being less likely to result in withdrawal symptoms.

[figure not shown]

Figure 19:a) Pharmacokinetics of repeated PF-04457845 administration in healthy human subjects. b) Pharmacodynamics of repeated PF-04457845 administration in healthy human subjects.

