12.1 Reporting Period: For SAEs, the active reporting period begins from the time that the participant provides informed consent, which is obtained prior to the participant's participation in the study, through the last follow up visit (end of study visit). Should an investigator be made aware of any SAE occurring any time after the active reporting period, it must be promptly reported.

12.2 Capturing Adverse Events: Safety and adverse events will be captured using the Systematic Assessment for Treatment Emergent Events (SAFTEE) general and specific inquiry forms, which take approximately 20 minutes to administer. Collection of adverse events will commence from the time the participant signs the informed consent to participate in the study and will continue until the last safety follow up visit. At each study visit, the investigator will

assess whether any subjective AEs have occurred. A neutral question, such as "How have you been feeling since your last visit?" may be asked. Participants may report AEs occurring at any other time during the study. All participants experiencing AEs, whether considered associated with the use of the study drug or not, must be monitored until the symptoms subside and any clinically relevant changes in laboratory values have returned to Baseline or until there is a satisfactory explanation for the changes observed. All AEs will be documented, whether or not the investigator concludes that the event is related to the drug treatment. Any medical condition that is present at the time that the participant is screened will be considered as baseline and not reported as an AE. However, if the study participant's condition deteriorates at any time during the study, it will be recorded as an AE.

The following information will be documented for each event:

- 1. Event term.
- 2. Start and stop date and time.
- 3. Pattern of AE (Frequency).
- 4. Intensity.
- 5. Investigator's opinion of the causal relationship between the event and administration of study drug(s) (related or not related).
- 6. Investigator's opinion of the causal relationship to study procedure(s), including the details of the suspected procedure.
- 7. Action concerning study drug.
- 8. Outcome of event.
- 9. Seriousness.

The different categories of intensity (severity) are characterized as follows:

- Mild: The event is transient and easily tolerated by the participant. The event does not
 generally interfere with usual activities of dailyliving.

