14.2.2 Secondary Outcomes: The same analytic strategy will be followed for secondary outcomes compared to the primary outcome. Primary analyses will be based on ANCOVA with multiple imputation on the modified intent-to-treat sample, secondary analyses will include mixed models, tipping point analyses and analyses of the per protocol sample. The emphasis will be on effect estimation. Testing in the primary analyses will be adjusted using the Bonferroni-Holm method. For each eCB, plasma levels will be assessed by fitting a mixed effects model with treatment, time, site, and the interaction terms as fixed effects, and tobacco use as covariate. Exploratory analyses will be conducted to assess the effect of variables such as gender and use of other substances on endocannabinoids. Since we expect floor effects for the blood levels of PF-04457845 in the placebo condition, PF-04457845 blood level will be assessed by using non-parametric models (226, 227) with treatment, time, site, and the interaction terms as factors.

14.3 Safety Analysis: The review and summary of safety will be performed on the modified intent-to-treat sample. Events or abnormalities will be searched from the time of the first dose until 5 half-lives after the last dose. Clinical laboratory data will be summarized quantitatively using descriptive statistics such as changes from baseline summarized by mean, standard deviation, median, minimum and maximum, and summarized qualitatively by tabulating clinical abnormalities. Vital signs, BMI, weight will be summarized using descriptive statistics. Group differences in the percentage of participants who report AEs or exhibit clinically significant changes during 1) 8-week treatment phase (from the first dose until the last dose), and 2) the 4-week follow up phase (to assess any lingering post treatment safety issues) will be summarized in tabular form and presented. Data permitting, exploratory analyses may be performed to evaluate the statistical significance of between-group differences (e.g. using Fisher's exact tests for adverse events, t-tests or non-parametric equivalent for changes in continuous measures) and evaluation of the effects of duration of drug exposure or drug dose on any adverse events (e.g. using exact logistic regression) and laboratory measures (e.g. using mixed effects models).

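### Section 14.3 ends the safety search 5 half-lives after the last dose (2.5 to 4.8 days at the stated half-life), while the same section and Table 10 report the whole 4-week follow-up

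*Combined protocol and SAP*

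**What the plan says.** Section 14.3 (Safety Analysis) opens with a time limit: "Events or abnormalities will be searched from the time of the first dose until 5 half-lives after the last dose". It names no half-life and gives no number of days. Later in the same paragraph, group differences in adverse events and clinically significant changes are to be tabulated for the 8-week treatment phase and for "the 4-week follow up phase (to assess any lingering post treatment safety issues"). Table 10 gives the same two periods for the safety endpoints.

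Other sections bear on the length of the window:

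- Section 12.2: adverse event collection "will continue until the last safety follow up visit".
- Section 3.2.1, repeated in 11.1.1: "Elimination of PF-04457845 is multi-phasic, with a half-life (t1/2) ranging from 12-23 hours".
- Section 3.2.2: "Pharmacological washout takes 10 days after multiple dosing with 4 mg". The protocol attributes this to drug clearance combined with recovery of FAAH activity.
- Section 11.1.1: "the drug and its effects persist for up to 2 weeks after last dose; this is the reason for the 4-week safety follow-up".
- Section 10.2.1 schedules the safety laboratory tests at "Screening, Week 1, Week, 5, Week 7, Week 9, and End of Study Visit (end of Week 12").
- Section 4.2.2: the laboratory and vital-sign endpoints count a participant with a markedly abnormal value on any occasion after dosing. No end date is given.

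**The concern.** The two sentences of 14.3 define different observation periods for the same kind of data. Nothing says that they serve different outputs. An analyst who applies the first drops most of the follow-up; an analyst who applies the second keeps it.

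The part dropped is what the follow-up was added to observe. It also contains the End of Study visit, the only scheduled safety laboratory panel and vital-sign measurement after Week 9. A clinically significant laboratory value is itself an adverse event under Section 12.0, so it could still reach the by-phase table. A value that is markedly abnormal but not judged clinically significant has no such route, although the endpoint counts it.

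The limit runs from each participant's last dose, so it closes early for anyone who stops the drug but stays in the study, as Section 8.1 allows.

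A smaller, separate matter is that 14.3 uses the modified intent-to-treat set for safety. Under Section 14.0 that set requires a baseline and a post-baseline measurement, so a dosed participant who lacks either is left out.

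**Working it through.** The plan never converts 5 half-lives to days, so there is no figure of its own to reproduce.

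**Inputs.** Half-life 12 to 23 h (3.2.1). Last dose on about day 56, the end of 8 weeks. Follow-up from day 57 to day 85, which is 28 days (Table 2). Follow-up visits after Week 9 on nominal days 64, 71, 78 and 85, each ± 3 days. Washout 10 days (3.2.2). Persistence up to 14 days (11.1.1).

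**Window at the stated half-life.** Length in days = 5 × t½ / 24.

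- 12 h: 60 h = 2.5 days, closing on day 58.5.
- 23 h: 115 h = 4.79 days, closing on day 60.8.
- Share of the follow-up covered: 2.5/28 = 8.9% to 4.79/28 = 17.1%, so 82.9 to 91.1% lies outside.
- The washout ends on day 66, which is 5.2 to 7.5 days after the window closes.
- All four later visits, at their nominal days, fall after the window. Events that start inside it and are reported later still count.

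**Other readings of the half-life.** Elimination is called multi-phasic, so a longer value could be argued. Both alternatives below are assumptions.

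*A. Effective half-life from accumulation.* Section 3.2.1 reports: "An approximate 2-3 fold accumulation in exposure was observed between days 1 and 14". For a one-compartment drug given once daily, R = 1/(1 − exp(−24k)). R = 2 gives t½ = 24.0 h; R = 3 gives t½ = 24 × ln 2 / ln 1.5 = 41.0 h.

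*B. The 14-day persistence taken as 5 half-lives.* t½ = 14 × 24/5 = 67.2 h.

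| Reading | t½ (h) | 5 × t½ (days) | Window closes (day) | Follow-up outside | Days short of day 85 |
|---|---|---|---|---|---|
| Stated, low | 12 | 2.5 | 58.5 | 91.1% | 26.5 |
| Stated, high | 23 | 4.8 | 60.8 | 82.9% | 24.2 |
| A, R = 2 | 24.0 | 5.0 | 61.0 | 82.1% | 24.0 |
| A, R = 3 | 41.0 | 8.5 | 64.5 | 69.5% | 20.5 |
| B | 67.2 | 14.0 | 70.0 | 50.0% | 15.0 |

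**Break-even half-life** = days × 24/5.

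- 10-day washout: 48.0 h, or 48/23 = 2.1 times the top of the stated range.
- 14 days: 67.2 h, or 2.9 times.
- Day 85 (29 days after day 56): 139.2 h, or 6.1 times. If that visit is 3 days early (26 days): 124.8 h, or 5.4 times.

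**Early stop.** With a last dose on day 28, the window closes on day 30.5 to 32.8. If the participant keeps the original visit calendar, the Week 7, Week 9 and End of Study panels (days 43, 57 and 85) are all outside.

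**The case against.** The strongest reply is that the document mostly settles which period governs. Table 10 puts the adverse event, laboratory and vital-sign endpoints under one outcome that covers both phases. Section 14.3 repeats those phases for the between-group percentages, and Section 4.2.2 sets no end date. Against these stands one general sentence that names no output, and it may have been meant only to define treatment-emergent events. On that view the loss is confined to a markedly abnormal value that is not clinically significant and is first seen on day 85.

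Much of this is fair. Table 10 is probably what was intended, and the residual is narrow if it prevails. But the search sentence covers events and abnormalities without qualification, does not mention a treatment-emergent flag, and is not subordinated to Table 10.

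Three further points limit the size of the finding:

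- The percentages outside the window are calendar time, not events.
- The 10-day washout is partly pharmacodynamic, so a shorter plasma window is not by itself a contradiction. It does show that plasma half-life is a poor measure of how long the drug acts.
- Section 8.1 also allows a participant who stops early to have Week 9 procedures attempted at termination and to enter the 4-week follow-up. On that route a panel could fall near or inside the window. The early-stop example applies only to those who continue the remaining scheduled procedures.

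Deleting the sentence would also remove the only text that could supply a cut-off for treatment-emergent events, which the document does not otherwise define. The fix therefore leaves room for one.

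**Conclusion.** The concern holds and should be fixed. Read literally, 14.3 ends the search 2.5 to 4.8 days after the last dose and leaves 83 to 91% of the follow-up days uncounted, including the day-85 laboratory and vital-sign measurements. The by-phase sentence in 14.3 and Table 10 count them.

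The figures assume the stated 12 to 23 h half-life and a last dose on day 56. The longer half-lives considered above reduce the share outside to between 50 and 82%, but day 85 stays outside under each of them.

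The effect on the reported percentages cannot be sized, because the document gives no rate of late events. Data collection, serious adverse event reporting, monitoring board review and the primary efficacy analysis are not affected. The analysis-set point is secondary and probably small; the number excluded is not given.

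**What to change.** In Section 14.3, delete the 5-half-life limit. State that events and abnormalities are counted from first dose through the End of Study visit and tabulated separately for the 8-week treatment phase and the 4-week follow-up, as Table 10 already specifies.

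If an on-drug window is wanted, for example to define treatment-emergent events, present it as an additional labelled summary and give its length in days or the half-life used.

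Separately, define the safety set as all randomised participants who took at least one dose, without the baseline and post-baseline requirement.

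The cost is wording only, since the data are already collected through day 85. A few more unrelated late events will be counted in both arms; the separate follow-up tabulation keeps them visible.

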Study Description:	The efficacy, safety and tolerability of the FAAH Inhibitor PF-0447845 in reducing cannabis use will be studied in a 4-site randomized, double-blind, placebo-controlled, parallel-group, outpatient clinical trial comparing PF-04457845 (4mg) and placebo in DSM-5 CUD individuals. Participants will be randomized in a 1:1 ratio to either PF-04457845 or placebo using random block sizes of 2 and 4, stratified by site and degree of cannabis use (CUD at the level of moderate (4-7 [of 11] symptoms) or severe (8-11 [of 11] symptoms)). Participants will receive motivational interviewing for 2 weeks before being randomized to receive study medication to make a quit attempt within the first week of treatment. For a self-reported quit attempt, participants will be rewarded. Participants will receive active or placebo PF-04457845 for 8 weeks during which time they will be evaluated weekly with either in person or remote study visits. In addition, daily assessment of adherence to study medication and cannabinoid use will be conducted by cellphone. Measures of cannabinoid exposure, and problems related to the use of cannabis, will be assessed.								
Primary Objective:	To determine whether PF-04457845 is superior to placebo in reducing self-reported frequency (number of times per day) of cannabis use.								
Primary Endpoint:	Change in the average number of times per day of self-reported cannabis consumption.								
Study Population:	Up to approximately 260 individuals diagnosed with DSM5 Cannabis Use Disorder								
Phase:	Phase 2B								
Description of Sites	This multi-center trial will take place at four sites: Yale University School of Medicine,								
Enrolling	Columbia University Medical Center, John Hopkins University, & Medical University of								
Participants:	South Carolina.								
Description of Study Interventions:	For 8 weeks participants will receive 4mg daily of PF-04457845 or placebo.								
Study Duration:	The duration of this study is approximately 3 years.								
Participant Duration:	This trial is 14 weeks total, including: 1) a 2-week screening phase, 2) randomization to PF-04457845 or placebo for 8 weeks, and 3) a 4 week follow up phase for safety especially because the effects of the drug take ~ 2 weeks to washout.								

1.4 Protocol Summary Schema:

Table 1: Schematic of Study Design

Screening				Treatment Phase Outpatient									Follow–up Phase					

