8.0 STUDY INTERVENTION DISCONTINUATION AND PARTICIPANT DISCONTINUATION/WITHDRAWAL

8.1 Discontinuation of Study Intervention: Discontinuation from PF-04457845 does not mean discontinuation from the study. Attempts will be made to complete the remaining study procedures as indicated by the study protocol. If a clinically significant finding is identified (including, but not limited to changes from baseline) after enrollment, the investigator or qualified designee will determine if any change in participant management is needed. Any new clinically relevant finding will be reported as an adverse event (AE). Every attempt should be made to collect the data that would be collected at a termination visit (Week 9 Visit) as listed in 1.5 Schedule of Procedures: Table 2. If the participant is prematurely withdrawn from the treatment phase, he/she may be entered into the 4-week follow up phase.

8.2 Participant Discontinuation/Withdrawal from the Study: Participants are free to withdraw from participation in the study at any time upon request. The investigator may discontinue a participant's study participation at any time during the study if the participant meets the study termination criteria. In addition, a participant may discontinue his or her participation without giving a reason at any time during the study.

8.2.1 Criteria for Discontinuation or Withdrawal of a Participant: The primary reason for discontinuation or withdrawal of the participant from the study or study drug should be recorded using the following categories.

- 1) Adverse Event: The participant has experienced an AE that requires early termination because continued participation imposes an unacceptable risk to the participant's health or the participant is unwilling to continue because of the AE.
- 2) *Important Protocol Deviation*: The discovery post-randomization that the participant failed to meet protocol entry criteria or did not adhere to protocol requirements, and continued participation poses an unacceptable risk to the participant's health.
- 3) *Lost to Follow-Up*: The participant did not return to the study site and multiple attempts to contact the participant were unsuccessful. Attempts to contact the participant must be documented.

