- Moderate: An AE that is usually alleviated with additional specific therapeutic intervention. The event interferes with usual activities of daily living, causing discomfort but poses no significant or permanent risk of harm to the research participant.
- Severe: An AE that interrupts usual activities of daily living, significantly affects clinical status, or may require intensive therapeutic intervention, and are usually potentially life-threatening or incapacitating. The term "severe" does not necessarily equate to "serious".

Note the distinction between the severity and the seriousness of an AE. A severe event is not necessarily a serious event. For example, a headache may be severe (interferes significantly with participant's usual function) but would not be classified as serious unless it met one of the criteria for SAEs, listed above.

Action Concerning the Study Drug: For every adverse event, the action taken concerning the study drug will be documented on the source document.

- Drug withdrawn: a study drug is stopped due to the particular AE.
- Dose not changed: the particular AE did not require stopping a study drug.
- Unknown: only use if it has not been possible to determine what action has been taken.
- Not Applicable: study drug was stopped for a reason other than the particular AE (the study has been terminated, the participant died, dosing with study drug was already stopped before the onset of the AE)
- Dose Interrupted: the dose was interrupted due to the particular AE.

12.3 Assigning Causality of Adverse Events: Causality to study procedures should be determined for all adverse events. The degree of certainty about causality will be graded using

the categories below. In a clinical trial, the study product must always be suspect.

- Definitely Related There is clear evidence to suggest a causal relationship, and other
 possible contributing factors can be ruled out. The clinical event, including an abnormal
 laboratory test result, occurs in a plausible time relationship to study intervention
 administration and cannot be explained by concurrent disease or other drugs or
 chemicals. The response to withdrawal of the study intervention (dechallenge) should be
 clinically plausible. The event must be pharmacologically or phenomenologically definitive,
 with use of a satisfactory rechallenge procedure if necessary.

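### The optional exploratory regression of adverse events on duration of drug exposure in Section 14.3 would not estimate an effect of exposure, and a dose term adds nothing with one active dose

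*Combined protocol and SAP*

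**What the plan says.** The last sentence of Section 14.3 opens "Data permitting, exploratory analyses may be performed to evaluate the statistical significance of between-group differences" and goes on to include "evaluation of the effects of duration of drug exposure or drug dose on any adverse events (e.g. using exact logistic regression"), with mixed models named for laboratory measures. The analysis is therefore permitted rather than promised, and the logistic model is an example. The text does not mention time at risk, time-updated exposure, a landmark, or what to do when an AE is the reason for stopping. It does not say whether dose means dose assigned or dose taken.

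Four other statements bear on it:

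- Search window, Section 14.3: "Events or abnormalities will be searched from the time of the first dose until 5 half-lives after the last dose". Section 3.2.1 describes elimination "with a half-life (t1/2) ranging from 12-23 hours".
- Dose, protocol synopsis: "For 8 weeks participants will receive 4mg daily of PF-04457845 or placebo".
- AEs can end participation or treatment, Section 8.2.1, first listed reason: "The participant has experienced an AE that requires early termination because continued participation imposes an unacceptable risk to the participant's health".
- AEs can stop the drug, Section 12.2, action concerning study drug: "a study drug is stopped due to the particular AE". The same list has a category for dosing interrupted because of an AE.

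The main safety summary in Section 14.3 is separate: the percentage of participants with AEs by randomised group, tabulated for the treatment and follow-up phases.

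**The concern.** Total duration of exposure is not fixed before the outcome is seen. It depends partly on the AE itself, because an AE may end or interrupt dosing. It also sets how long a participant is searched for AEs, because the window closes a few days after the last dose. Both links act even if the drug has no effect on AEs and the hazard never changes.

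The coefficient therefore reflects how often AEs lead to stopping and how long people were watched. An odds ratio above 1 could be reported as harm accumulating with longer treatment. One below 1 could be reported as tolerance developing. For an unapproved drug intended for repeated dosing, either statement could carry into later planning without evidence behind it.

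**Working it through.** **1. Size of the active arm.** Section 14.1 gives d = 0.42, 80% power and two-sided alpha 0.05. Per arm: 2 × (1.960 + 0.842)² / 0.42² = 89, so 178 in total, as stated. With 25% dropout: 178 / 0.75 = 237.3, against the stated 237. Half of that, rounded up, is 119 in the active arm. Section 14.3 has no figure of its own to reproduce.

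**2. Search window.** Five half-lives are 5 × 12 h = 2.5 days to 5 × 23 h = 4.8 days. I used 3.6 days after the last dose.

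**3. Upward bias by hand.** Suppose no AE stops treatment and 50% have an AE by day 56 (assumption). The hazard is ln 2 / 56 = 0.01238 per day. The chance of a recorded AE after exposure of T days is 1 − exp(−0.01238 × (T + 3.6)).

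- Two weeks: 1 − exp(−0.01238 × 17.6) = 0.196, odds 0.243.
- Eight weeks: 1 − exp(−0.01238 × 59.6) = 0.522, odds 1.091.
- Ratio of odds: 1.091 / 0.243 = 4.48 over six weeks, or 4.48^(1/6) = 1.28 per week.

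The hazard is the same throughout. The 1.28 comes only from longer observation.

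**4. Both biases together.** I simulated 1,000 null trials per setting, with 119 active participants, constant AE hazard, 25% other dropout over 56 days and the window above. A first AE stops the drug with probability q. AE (yes/no) is regressed on weeks of exposure. The odds ratio is the median of 300 fits. The rejection rate uses the large-sample form of the exact conditional test at nominal 5%. The AE rates and q are assumptions, not figures from the documents.

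| AE by 8 weeks | q | Odds ratio per week | Falsely significant |
|---|---|---|---|
| 20% | 0 | 1.26 | 24%, all upward |
| 20% | 0.1 | 1.10 | 7%, nearly all upward |
| 20% | 0.3 | 0.94 | 12%, nearly all downward |
| 20% | 0.5 | 0.85 | 45%, all downward |
| 50% | 0 | 1.31 | 78%, all upward |
| 50% | 0.1 | 1.14 | 31%, all upward |
| 50% | 0.3 | 0.97 | 6% |
| 50% | 0.5 | 0.88 | 50%, all downward |
| 70% | 0 | 1.37 | 92%, all upward |
| 70% | 0.5 | 0.91 | 27%, nearly all downward |

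The two biases roughly cancel at q of 0.2 to 0.3. A fresh run of 400 trials per setting gave the same pattern (at 50%: 1.30, 1.14, 0.97 and 0.88).

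**5. Which end is likelier.** Section 3.3 reports that 51% on PF-04457845 had an AE in a 2-week treatment study and that nobody was permanently withdrawn for one. That is frequent AEs with q near 0, the upward end of the table.

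**6. Dose.** With assigned dose coded 0 or 4 mg, the dose term is the arm term divided by four. In a worked example, 4 × β(dose) = β(arm) = 0.429, with the same p = 0.102. Within the active arm assigned dose has zero variance, so nothing can be estimated.

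**7. The alternative under the same null.** I used 600 trials, 238 randomised, q = 0.2, and AE rates of 20, 50 and 70%. First-event rate by week among those still on drug, with a person-time offset, gave a rate ratio of 1.00 per week and rejection of 4.2 to 5.3%. The randomised comparison of AE rates per person-time rejected in 4.5 to 5.8%.

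**The case against.** The strongest reply is that little rests on this clause. It is optional, exploratory and conditional on the data, and exact logistic regression is only an example. The safety endpoints in Section 4.2.2 are percentages by arm. Neither the stopping rules in Section 8.4 nor the data and safety monitoring board review in Section 16.5 refers to it. All of this stands. A reader might infer that the plan commits to the regression or that the trial's safety conclusions depend on it. The documents support neither.

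A reader might also infer that the dose term is an artefact. For assigned dose it is not: 0 against 4 mg is the randomised comparison, valid but redundant. Only dose actually taken, which varies and is tracked under Section 7.6, would share the duration problem, and the plan does not say which is meant.

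Third, a reader might infer that a falsely protective and a falsely harmful result are equally likely. In the settings tried, a clearly downward result needs roughly 30% or more of first AEs to end treatment, and the documents do not suggest that. If the 51% seen in the 2-week study held at a constant hazard, 1 − 0.49⁴ = 94% would have an AE by 8 weeks, and the odds ratio would stay above 1 (about 1.07) even at 50% stopping. That extrapolation is rough, but it points the same way as the withdrawal record.

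Finally, with no AE-driven stopping, an odds ratio above 1 correctly says that cumulative risk grows with time. That is fair, but it holds at any constant hazard, placebo included, so it is not evidence that longer exposure raises risk. Extending the search does not cure the problem: with a fixed 84-day window, 50% AE and 30% stopping, the odds ratio was 0.86 and 42% of null trials were significant.

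**Conclusion.** The point holds for duration and, in a narrower sense, for dose. A logistic regression of AE on total exposure would not recover a null duration effect except where the two biases happen to cancel. Under a constant hazard its odds ratio per week ran from about 1.3 with no AE-driven stopping to between 0.85 and 0.91 at 50% stopping. These sizes rest on assumed AE rates of 20 to 70%, assumed stopping probabilities and the documents' 25% dropout. The more probable error is a false signal of harm with longer treatment. For assigned dose the defect is redundancy between arms and non-estimability within the active arm. The consequence is confined to an exploratory safety statement. The by-arm AE percentages, the efficacy analysis and the stopping rules are untouched.

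**What to change.** Amend the one clause in Section 14.3.

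1. Drop the assigned-dose term for AEs. If dose taken is intended, define it and treat it as time-updated exposure.
2. Replace logistic regression on total duration with a person-time or time-to-first-event analysis. Report participants with a first event per person-week at risk, by arm, with 95% confidence intervals. For the duration question, report the first-event rate by period on treatment (for example weeks 1–2, 3–4 and 5–8) among those still at risk, or fit a model with time-updated exposure.
3. Keep the by-arm AE percentages as the main safety contrast, and leave the laboratory mixed models as they are.

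AE start and stop dates are already recorded under Section 12.2, so no new data are needed. The cost is one clause and a little more programming on an exploratory analysis.
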